6.8 Dose Escalation Assessments

Every 5 (+ 2) days through Week 7, just prior to each dose escalation assessment, parent/legal guardian will be asked to measure HR and BP using the device given to them from the study team at the time of randomization. A telephone or in-person assessment by the treating clinician will occur to determine dose escalation. If the participant reaches the maximum dose of 3 mg/day, prior to Week 7, no dose escalation will occur. Alternatively, a CGI-I will be determined by the treating clinician and any score of 3 or worse (higher) will warrant dose escalation, provided no significant safety concerns exist. AEs and safety ESIs will be recorded to assess safety.

Clinically significant findings that would prevent dose escalation include, but are not limited to:

- CGI-I score of 2 or 1
- HR and BP values that are considered unsafe to dose escalate:
 - Clinically significant hypotension, defined as systolic BP percentile less than the 5th percentile.^{31,34} This corresponds to systolic BP percentiles for neurotypical children under the 8th percentile for males and under the 10th percentile for females.
 - Clinically significant bradycardia, defined as HR > 2 SD below mean for age
- Any AEs or safety ESIs that make it unsafe to dose escalate, at the discretion of the treating clinician
- Any other finding that indicates it is not safe to dose escalate, at the discretion of the treating physician and/or principal investigator (PI).

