6.13 Dosage and Study Drug Information

6.13.1 Dose Timing

Dose escalation

Study product will be administered once daily (q.h.s.) during the first 5 (+ 2) days of study product administration and then twice daily thereafter. Twice daily doses may be administered in uneven BID dosing; for example, a total daily dose of 2.0 mg can be divided into 0.5 mg in the morning and 1.5 mg in the evening, at the discretion of the clinical provider. Dose escalation will occur based on the details in **Table 3** with the highest dose being dose level 6. Participants in both the GIR and placebo arms will be evaluated for potential dose escalation every 5 (+ 2) days via a Dose Escalation Assessment (via telephone during Weeks 1-3 and 5-7 or in-person at Week 4) described in Section **6.8**. Parent/legal guardian will be asked to measure HR and BP prior to each dose escalation assessment. If there is a safety concern during the weekly Dose Escalation Assessments (via telephone during Weeks 1-3 and 5-7 or in-person at Week 4) as stated in Section **6.8**, or for any other reason, the sites will be instructed on the following:

1. Hold at current dose/schedule for 5 (+ 2) days (or advance directly to step #3 or step #5 below, if deemed appropriate by the clinical provider)

2. Reassess at next dose-escalation assessment
3. If sedation is a significant concern, divide the total daily dose and give higher dose proportion at bedtime (q.h.s); example: 2 mg totally daily dose split as 0.5 mg in the morning and 1.5 mg q.h.s and
4. Reassess at next dose-escalation assessment
5. If safety concern remains, reduce total daily dose to the lower dose previously tolerated

Table 3. Dose Escalation Plan*

Dose Level	Total daily dose for weight \geq 25 kg (mg)
1	0.5
2	1.0
3	1.5
4	2.0
5	2.5
6	3.0

* Parent/legal guardian will be asked to measure HR and BP prior to each dose escalation assessment.

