7.1.2 Safety Events of Special Interest (ESIs)

A safety ESI is a select safety event that could be related to the study drug. Safety ESIs will be solicited for their occurrence (No or Yes) at weekly dose-escalation assessments, including in-person assessments (Week 4 and Week 8), and the final telephone safety assessment (5 + 2 days) after the final dose of study drug. The safety ESIs documented will be assessed by the investigator/delegate (defined as a clinician licensed to make a diagnosis) for intensity, causality, and association to provide uniform data collection of all events. Any reported ESIs should be managed, as needed, according to clinical judgement and local guidelines.

Safety ESIs include:

- Syncope/passing out
- Sedation
- Trouble falling asleep
- Trouble staying asleep
- Trouble waking up
- Drowsiness
- Decreased Energy/Fatigue
- Trouble concentrating
- Trouble breathing
- Constipation
- Diarrhea
- Nausea
- Vomiting
- Skin rash
- Itching
- Change in appetite
- Anxious/fearful

- Sadness/depressed mood
- Self-injurious behavior
- Clinically significant hypotension, defined as systolic BP percentile less than the 5th percentile.^{31,34} This corresponds to systolic BP percentiles for neurotypical children under the 8th percentile for males and under the 10th percentile for females.
- Clinically significant bradycardia, defined as HR > 2 SD below mean for age

The following safety ESIs will only be assessed at in-person visits (Week 4 and Week 8):

- Any clinically significant cardiac event (e.g., clinically significant changes on ECG)
- Suicidality via the asQ Tool (see Section [6.10](#))

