10.4.2 Secondary Analysis

Safety profile of GIR will be presented using AEs and solicited safety ESIs. Number of AEs, SAEs, and SUSARS will be summarized by treatment group (GIR vs. placebo) and overall, by severity, and by each Medical Dictionary for Regulatory Activities (MedDRA®) system organ class and preferred term.

Incidence of safety ESIs will also be presented by treatment group (GIR vs. placebo) and overall. Additional model based analyses of safety ESIs will be performed to estimate treatment effect adjusted for baseline covariates and cumulative dose.

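### Section 10.4.2 adjusts the ESI treatment effect for cumulative dose, which ESIs and response themselves change, so the adjusted coefficient is not the as-randomised effect

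*Combined protocol and SAP*

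**What the plan says.** Section 10.4.2 plans two things for the safety events of special interest (ESIs). The first is descriptive: "Incidence of safety ESIs will also be presented by treatment group (GIR vs. placebo) and overall". The second is a model: "Additional model based analyses of safety ESIs will be performed to estimate treatment effect adjusted for baseline covariates and cumulative dose". The model is a commitment. By contrast, section 10.4.1 lists cumulative dose for the primary ABC-H model only among covariates that may be examined.

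Three other sections determine what cumulative dose is.

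- Section 6.8 lists findings that prevent escalation. They include "Any AEs or safety ESIs that make it unsafe to dose escalate, at the discretion of the treating clinician", and also a CGI-I of 1 or 2.
- Section 6.13.1 sets out the response to a safety concern: hold, reassess, for sedation shift more of the same daily dose to bedtime, and finally "If safety concern remains, reduce total daily dose to the lower dose previously tolerated". Clinicians may skip ahead in this sequence.
- Section 6.13.1 applies the titration to everyone: "Participants in both the GIR and placebo arms will be evaluated for potential dose escalation".

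On collection, section 7.1.2 says "Safety ESIs will be solicited for their occurrence (No or Yes) at weekly dose-escalation assessments". No section says how cumulative dose is computed for a child on placebo.

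**The concern.** Randomisation protects a comparison adjusted for baseline variables. It does not protect one adjusted for a variable that forms during follow-up and that the outcome helps to set. A child with troublesome ESIs is held or reduced and so accrues less dose. A child who responds on CGI-I stops escalating and also accrues less. Cumulative dose is thus partly a consequence of the ESIs being analysed and partly a consequence of treatment. Conditioning on it breaks the randomised comparison.

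The safety profile is the secondary objective (section 3), and this is the only ESI model the plan names. If its arm coefficient is reported as the treatment effect, a reader could be told that sedation is less, more or differently related to guanfacine than the randomised data show.

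**Working it through.** **The plan's own figure.** No power or precision is stated for ESIs. The only sample-size statement (section 10.6, ABC-H, d = 0.90) reproduces: 82.1% power at 32:16, and 48/0.8 = 60. It has no bearing on this point.

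**Why the coefficient moves.** Let y be a child's share of assessments with an ESI, A the arm and D cumulative dose. For least squares, exactly,

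b_adj = b_unadj - g × d,

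where g is the coefficient on D given arm and d is the difference in mean D between arms.

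- Capsule coding: d is the GIR-minus-placebo difference in capsules, negative if GIR children stop or hold more often.
- 0-mg coding: d is the whole GIR mean, so it is large and positive, and g comes from the GIR arm alone.
- The sign of g is not fixed. It is negative if ESIs lower dose, and positive if higher dose raises ESI risk strongly enough.

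The two codings therefore tend to move in opposite directions from each other, but which one goes up depends on g.

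**Inputs.** From the documents: 60 children at 2:1 (40 and 20), six dose levels, and the titration rules. The base case uses 9 on-treatment assessments. Spacing of 5 days gives Days 6 to 46 (9) plus Week 8 = 10; spacing of 7 days gives Days 8 to 43 (6) plus Week 8 = 7. Assumed, because the documents give no values: ESI rates of 25% vs 10% per assessment (true difference 0.15), a logit-scale child effect with SD 1 or 2, the clinician responses, and the CGI-I stopping chances.

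**Adjusted arm difference, truth 0.15 (SD 1 / SD 2):**

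| ESI risk and dose | ESIs that hold / lower dose | CGI-I stopping, GIR vs placebo | Capsules | Placebo = 0 mg |
|---|---|---|---|---|
| unrelated | all / 30% | 15% vs 5% | 0.075 / 0.035 | 0.36 / 0.46 |
| unrelated | half / none | 15% vs 5% | 0.13 / 0.11 | 0.24 / 0.30 |
| unrelated | all / 30% | equal | 0.12 / 0.10 | 0.41 / 0.54 |
| +1.0 log-odds per level | all / 30% | 15% vs 5% | 0.19 / 0.13 | -0.09 / 0.11 |
| +1.0 log-odds per level | half / none | 15% vs 5% | 0.21 (SD 1) | -0.21 (SD 1) |

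In the first row at SD 1 the unadjusted value is 0.151. So g × d = 0.151 - 0.075 = 0.076 for capsules, and 0.151 - 0.355 = -0.204 for 0 mg. With half of ESIs holding, none lowering and equal CGI-I stopping, capsule coding gives 0.146 / 0.142, which is nearly unbiased. At +0.6 log-odds per level, with the first row's other settings and SD 1, it gives 0.154.

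**No drug effect on ESIs** (10% or 20% in both arms, first-row dose rules, CGI-I stopping 15% vs 5%). The unadjusted false-positive rate is 0.04 to 0.05. Capsule coding gives -0.02 to -0.07 with a rate of 0.09 to 0.20. The 0-mg coding gives +0.08 to +0.27 with a rate of 0.29 to 0.67.

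**Logistic check on ever having an ESI** (8 weekly steps, weekly CGI-I stopping 8% vs 3%, risk unrelated to dose):

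| Incidence; ESIs acted on | Unadjusted OR | Capsules | 0 mg |
|---|---|---|---|
| 62% vs 41%; 90% | 2.33 | 1.82 | 14.4 |
| 62% vs 41%; 50% | 2.35 | 2.11 | 5.81 |
| about 40% in each; 90% | 1.01 | 0.84 | 3.97 |

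If ESIs never alter dose and risk does not depend on dose, adjustment changes nothing (2.38 vs 2.39 with capsules).

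**The case against.** The strongest reply is that the model is additional. Incidence by arm is the stated endpoint (sections 3 and 10.2.2) and is presented regardless, so the randomised comparison survives. This stands, and it limits the harm to the model.

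A second reply is that the bias may be small. Section 6.8 blocks escalation only for ESIs that the clinician judges unsafe. The list in section 7.1.2 includes itching and diarrhea, and for sedation section 6.13.1 offers a split of the same daily dose before a reduction. This also stands for capsule coding, as the milder scenarios show. It does not rescue 0-mg coding, and the plan does not choose between the two.

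A third reply is that section 10.4 leaves detail to a later SAP. That covers the outcome form, dose coding and lagging. It does not cover the adjustment set, which section 10.4.2 has already fixed.

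A reader might also infer that, with incidence as the only named ESI display, early sedation that fades cannot be told from late sedation. The arithmetic behind this is right. Weekly risks of 0.40, 0.15, 0.05, 0.02 and then 0 give 1 - 0.60 × 0.85 × 0.95 × 0.98 = 52.5%. Risks of 0.02, 0.05, 0.10, 0.20 and 0.30 in the last five weeks give 1 - 0.98 × 0.95 × 0.90 × 0.80 × 0.70 = 53.1%. But the documents do not show that the time course will be lost. Most ESIs are recorded yes or no at each assessment, table detail is left to the SAP, and the parent-completed ESS-CHAD at Day 1, Week 4 and Week 8 gives a partial view of persisting sleepiness, though none of Weeks 1 to 3. A by-assessment table is a useful addition, not the repair of an error.

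**Conclusion.** The concern holds for the model. An arm coefficient adjusted for cumulative dose does not estimate the as-randomised ESI effect, because ESIs and CGI-I response both feed into cumulative dose under sections 6.8 and 6.13.1.

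The error's size and direction are not known in advance. For a true difference of 0.15 and CGI-I stopping of 15% vs 5%, the scenarios ran from about 0.04 to 0.21 with capsules and from about -0.21 to +0.46 with placebo at 0 mg. These are illustrations under assumed rates, not bounds: equal stopping took the 0-mg figure to 0.54. With no drug effect on ESIs and unequal CGI-I stopping, either coding can produce a spurious arm difference.

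A reader might infer that capsule coding always hides a real effect and 0-mg coding always inflates it. The documents do not support this. That pattern requires ESI risk to be unrelated to dose between 0.5 and 3 mg, which nothing in the protocol says, and at +1.0 log-odds per level with SD 1 it reverses. Nor is it right that both codings must be biased: capsule coding is close to unbiased when CGI-I stopping is equal and few ESIs change the dose.

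Confidence is high on the adjustment set and low on any particular magnitude.

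**What to change.** In section 10.4.2, and in the SAP, estimate the model-based ESI treatment effect adjusted for baseline covariates only. Move any model containing cumulative dose to the exposure-response work in section 10.4.3, label it supplementary, state how placebo dose is coded, and do not report its arm coefficient as the treatment effect. Dose before each assessment suits that purpose better than the total over the trial. The cost is one term removed from one model, with no new data, visits or participants.

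Optional: alongside the incidence table, add a descriptive table of ESIs by assessment and arm, with denominators and current daily dose. Cardiac events and suicidality would appear only at the Week 4 and Week 8 in-person visits. The data are already collected. The cost is one more table, with wide intervals at single assessments: the 95% half-width 1.96 × sqrt(p1(1-p1)/40 + p0(1-p0)/20) is about 19 points at 25% vs 10%. No added test is needed.

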10.4.3 Exploratory Analysis

Exploratory Analysis 1: Characterize GIR exposure in children with DS.

The dosing, sampling, and demographic information collected by the study will be merged with bioanalytical information to create a PK dataset for GIR. Because a sparse sampling scheme will be employed in this study, population PK will be used to characterize GIR PK. If a relationship between exposure and response is observed, population PK or exposure-response models may be developed.

A detailed description of PK/PD analyses will be described in the PK Analysis Plan. Briefly, the following analyses are anticipated depending on the adequacy of the collected data:

Population PK Analysis

Pharmacokinetic (PK) models for the pooled concentration data of GIR will be explored by non-linear mixed effects modeling using NONMEM or Phoenix NLME software. Appropriate compartmental models will be examined, and between-participant variability on model parameters will be explored. Covariate analysis will examine the correlation between model parameters with demographic factors (e.g., weight, body mass index (BMI), sex, race, lab values, and obesity status) and co-administered medications. Appropriate covariates will be incorporated into the model using a standard forward-addition backward-elimination technique. Standard model diagnostic plots and procedures will be used to evaluate model appropriateness. Empiric Bayesian estimates of individual participant PK parameters will be generated from the final model. Model evaluation will be performed by visual predictive check and bootstrapping procedures, as needed.

As appropriate, the following apparent PK parameters may be estimated at steady state: systemic clearance (CL_{ss}/F), volume of distribution (V/F), maximum concentration ($C_{max,ss}$), minimum concentration ($C_{min,ss}$), half-life ($t_{1/2}$), and area under the curve (AUC_{ss}/F). Other PK parameters may be estimated according to the adequacy of sampling.

Exploratory Analysis 2: Characterize the exposure-response relationship of GIR for the treatment of hyperactivity/impulsivity, inattention, and sleep quality in children with DS.

Exposure-Response (ER) Analysis:

A population ER analysis may be performed to characterize the PK/ER relationship between GIR exposure (e.g., $C_{max,ss}$, AUC_{ss}) and selected safety and efficacy endpoints (e.g., hyperactivity, impulsivity, inattention, or sleep quality in children is observed). The sleep quality will be assessed via the CSHQ and ESS-CHAD (see **Table 5**). These are continuous outcomes that will be analyzed similar to the primary outcome using a mixed effects model. Epworth Sleepiness Scale for Children and Adolescents (ESS-CHAD) will also be analyzed as a dichotomous outcome; scores ≥ 10 are “sleepy” and scores <10 are “normal” using a generalized linear mixed model with binary distribution and logit link.

Table 5. Distribution of Scales for Exploratory Outcome Sleep Quality Measures (CSHQ and ESS-CHAD)

Scale	Distribution of Outcome Scale	Outcome Values
Child's Sleep Habits Questionnaire (CSHQ, Abbreviated Version)	Continuous	Minimum Total Score: 33 Maximum Total Score: 99
Epworth Sleepiness Scale for Children and Adolescents (ESS-CHAD)	Continuous	Minimum Total Score: 0 Maximum Total Score: 24

Different PK/ER models, including logistic regression model for binary safety outcomes, efficacy outcomes, and linear, log-linear, and E_{max} models for continuous safety/efficacy outcomes, may be explored. The ER model development, evaluation, and validation will be similar to that described above for population PK model.

10.5 Demographics and Baseline Characteristics

The number of participants who either completed or discontinued early from the study will be summarized. Demographic and baseline characteristics will be summarized and compared between the study drug and placebo arms. Study product administration will be summarized in terms of number of days of dosing.

10.6 Sample Size Considerations

The primary hypothesis is that change from baseline on ABC-H subscale over the 8-week trial will be greater in GIR compared to placebo. In a randomized clinical trial of GER in ASD,¹⁵ the guanfacine group showed a 43.6% decline in scores on the ABC-H subscale (mean scores of 34.2 at baseline to 19.3 at week 8 visit) compared with a 13.2% decrease in the placebo group (mean scores of 34.2 at baseline to 29.7 at week 8 visit; effect size Cohen's $d=1.67$). Modal doses of GER in this trial were 3 mg/day (range 1 mg/day to 4 mg/day). In another single arm GIR trial,⁶ Capone et al. reported a mean decline in ABC-H scores from baseline to follow-up of 25% (mean scores of 29 at baseline to 21.2 at follow-up visit, Cohen's $d = 0.9$) over an average of 21 weeks. Average doses of GIR in the Capone study were 1.1 (± 0.5) mg/day, reflecting the more conservative approach to dose escalation in this patient population with DS. A decline in the ABC-H scale scores in the guanfacine group ranged from 25% to 43% across these studies. Although there are no identified studies characterizing a "clinically meaningful change" in ABC-H scores, the open-label Capone study revealed a significant improvement in target behaviors characterized as "inattention" and "activity" with the associated 25% improvement in ABC-H scores.⁶

Based on these studies, a conservative effect size of Cohen's $d = 0.9$ was assumed for the current randomized trial, which will be equivalent to assuming a 31.3% decline in the guanfacine arm (mean scores of 30 at Baseline to 20.6 at Week 8, $SD = 6$) compared with a 13.3% decrease in the placebo arm (mean scores of 30 at Baseline to 26 at Week 8, $SD = 6$). A sample size of 48 will achieve greater than 80% power to reject the null hypothesis of zero effect size when the population effect size is 0.90 and the significance level (alpha) is 0.050 using a two-sided two-sample equal-variance t-test. If a 20% dropout is assumed, N=60 participants will need to be enrolled.

11 FUTURE USE OF STUDY RECORDS AND BIOLOGICAL SPECIMENS

The medical data and study information entered in the participant's medical records will be kept per individual site policies for medical record retention. Other study records held at the study site will be kept until the FDA has completed any necessary review of the study results, or for a minimum of 2 years after the study has ended – whichever is longer. The research data collected in this study, and provided to the sponsor, will be kept indefinitely.

Information about this study, including study results, will be published without further permission from the participant as detailed in the informed consent form (ICF). Participants will not be identified in any publications or presentations made about the study.

After the study is completed, information about the study, including study data, will be submitted to the NIH data repository (<https://dash.nichd.nih.gov> and referred to below as "DASH"). With NIH approval, the data submitted to DASH may be used by other researchers for future research. The study data submitted to DASH will be de-identified, meaning it will not include any information that can identify the participant. The study team may also share the de-identified study data with other researchers. When the participant's de-identified study data are provided to other researchers for the purposes of future research, it will be done without obtaining additional permission from the participant.

Biological specimens collected for study-specific testing will be labeled at the site with a study-provided barcode label. The specimen labels will only contain a unique code number; it will not include protected health information (PHI) or any other information that could identify the study participant. Specimens will be stored at the site and then shipped to a central lab for study-specific testing. After analysis, specimens will be stored until the FDA completes review of the final research study report and proposed drug label changes. Once FDA review of the study results is complete, and after consent for future use of these specimens is confirmed, the specimens will be submitted to an NIH storage facility. With NIH approval, the de-identified study specimens may be made available to other researchers for future research without obtaining additional permission from the participant. Although whole genome sequencing (WGS) is not part of this study, study specimens containing genetic materials, may be made available to other researchers who may conduct WGS in the future. The participant's study specimens will not be sold to anyone; however, the use of these specimens may result in commercial profit. There is no provision to provide the participant with financial compensation beyond what is described in the ICF. Biological specimens may be stored indefinitely. If a participant decides to withdraw permission to use their study data or specimens, they will be instructed per the ICF to contact the site investigator. Study data and samples that have been recorded / collected prior to withdrawal will continue to be used, but no new data or specimens will be collected.

